Time unit

A year length is defined as 365.25 days. A month length is 30.4375 days (365.25/12). If duration is reported in months, duration in days will be divided by 30.4375. If duration is reported in years, duration in days will be divided by 365.25.

Baseline

For efficacy evaluations, the last non-missing assessment, including unscheduled assessments on or before the date of randomization is taken as "baseline" value or "baseline" assessment. In the context of baseline definition, the efficacy evaluations also include PRO.

For safety evaluations, the last available assessment on or before the date of start of study treatment is defined as "baseline" assessment. In the rare case that time of assessment and time of treatment start is captured, the last available assessment before the treatment start date/time is used for baseline.

If patients have no value as defined above, the baseline result will be missing.

On-treatment assessment/event and observation periods

For safety reporting the overall observation period will be divided into three mutually exclusive segments:

- 1. *pre-treatment period*: from day of patient's informed consent to the day before first administration of study treatment
- 2. *on-treatment period*: from date of first administration of study treatment to 30 days after date of last actual administration of any study treatment (including start and stop date). For crossover patients who start crossover therapy prior to last dose + 30 days, the on-treatment period will end on the day before the first dose of crossover treatment.
- 3. *post-treatment period*: starting at day 30+1 after last administration of study treatment.

Novartis	Confidential	Page 15
SAP	30-Sep-2021 (6:19)	CDRB436G2201

Notes: if data on clock time is available in the clinical database (e.g. for time of blood/urine sample taken, ECG performed, etc. and first study treatment administration), a more precise distinction between pre-treatment and on-treatment periods is encouraged to be used. If dates are incomplete in a way that clear assignment to pre-, on-, post-treatment period cannot be made, then the respective data will be assigned to the on-treatment period.

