2.4 Treatments (study treatment, rescue medication, concomitant therapies, compliance)

2.4.1 Study treatment / compliance

Duration of exposure, actual cumulative dose, dose intensity (DI) and relative dose intensity (RDI) will be summarized by treatment group, separately for each component of study treatment (dabrafenib, trametinib, carboplatin, and vincristine). The duration of exposure will also be presented for the study treatment. Duration of exposure will be categorized into time intervals; frequency counts and percentages will be presented for the number (%) of patients in each interval. The number (%) of patients who have dose reductions or interruptions, and the reasons, will be summarized by treatment group.

Patient level listings of all doses administered on treatment along with dose change reasons will be produced.

The Safety set will be used for all summaries and listings of study treatment.

Duration of exposure to study treatment

Duration of exposure to study treatment is considered by taking into account the duration of exposure to any combination partner.

Duration of exposure to study treatment (days) = (last date of exposure to study treatment) - (date of first administration of study treatment) + 1.

The last date of exposure to study treatment is the latest of the last dates of exposure to any combination partner (see Table 2-7 Definition of last date of exposure of study drug).

Summary of duration of exposure of study treatment in appropriate time units based on clinically meaningful time intervals (eg 8-<24, 24-<56, 56-<112, \geq 112 (weeks)) will include categorical summaries and continuous summaries (i.e. n, mean, standard deviation, median, 25th-75th percentiles, minimum, and maximum) using appropriate units of time.

Duration of exposure to combination partner

Duration of exposure to dabrafenib (days) = (last date of exposure to dabrafenib) – (date of first administration of dabrafenib) + 1.

Novartis	Confidential	Page 26
SAP	30-Sep-2021 (6:19)	CDRB436G2201

Duration of exposure to trametinib (days) = (last date of exposure to trametinib) – (date of first administration of trametinib) + 1.

Duration of exposure to carboplatin overall (days) = (last date of exposure to carboplatin as defined in table 2.7) – (date of first administration of carboplatin) + 1.

Duration of exposure to vincristine overall (days) = (last date of exposure to vincristine as defined in table 2.7) – (date of first administration of vincristine) + 1.

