
Induction phase:

Carboplatin is dosed as weekly IV infusions on weeks 1 to 4, and on weeks 7 to 10 followed by 2 weeks of rest in the *induction phase*. Vincristine is dosed as weekly IV bolus infusion for 10 weeks followed by 2 weeks of rest in the *induction phase*. The induction phase refers to the first 12 weeks of dosing (i.e from day of first dose of carboplatin or vincristine until 84 days).

The *last date of exposure* to carboplatin or vincristine in the induction phase is calculated including the rest periods (2 weeks). If subjects continued on to maintenance therapy, the last date of exposure in induction phase is the day before the start of maintenance therapy. If the subject does not continue on to maintenance therapy, the last date of exposure is calculated using the planned cycle duration, i.e. the last date of exposure is the date of first administration (of carboplatin or vincristine) in induction + 83 days. If the subject dies or if the data cutoff date is prior to the calculated date of last exposure, the date will be capped at the date of death or data cutoff. Maintenance phase:

Maintenance phase will continue for up to a total of 8 cycles, each cycle will be 6 weeks in duration and consists of 4 weekly doses of carboplatin followed by 2 weeks of rest, and three weekly doses of vincristine given concomitantly with the first 3 weeks of carboplatin , followed by three weeks of rest. The maintenance phase refers to the dosing after the first 12 weeks, and will be identified by having at least 9 non-zero doses of Carboplatin, or at least 11 non-zero doses of Vincristine. For Carboplatin/Vincristine, maintenance cycle week1 dates are defined by the following non-zero doses: dose 9/dose 11, dose 13/dose 14, dose 17/dose 17, dose 21/dose 20, dose 25/dose 23, dose 29/dose 26, dose 33/dose 29, and dose 37/dose 32, respectively.

The *last date of exposur* to carboplatin or vincristine in the induction phase is calculated including the rest periods (2 or 3 weeks). The last date of exposure is calculated using the planned cycle duration, i.e. the last date of exposure is the date of last week 1 administration (of carboplatin or vincristine) in maintenance +41 days. If the subject dies or if the data cutoff date is prior to the calculated date of last exposure, the date will be capped at the date of death or data cutoff. The *number of cycles* of maintenance therapy will be determined as the following total number of non-zero doses:

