 Carboplatin: 1 cycle - 9 to 12 doses; 2 cycles - 13-16 doses; 3 cycles - 17 to 20 doses; 4 cycles - 21 to 24 doses; 5 cycles - 25 to 28 doses; 6 cycles - 29 to 32 doses; 7 cycles - 33 to 36 cycles; 8 cycles - ≥ 37 doses.

Novartis	Confidential	Page 27
SAP	30-Sep-2021 (6:19)	CDRB436G2201

 Vincristine: 1 cycle - 11 to 13 doses; 2 cycles - 14-16 doses; 3 cycles - 17 to 19 doses; 4 cycles - 20 to 22 doses; 5 cycles - 23 to 25 doses; 6 cycles - 26 to 28 doses; 7 cycles - 29 to 31 cycles; 8 cycles - ≥ 32 doses.

Duration of exposure to carboplatin and vincristine (days) will be calculated by treatment phase (induction and maintenance phase) and overall (if applicable) as:

Duration of [study drug] exposure (days) in induction phase = (Date of first week1 dose of [study drug] in maintenance -1 day) - (date of first administration of [study drug]) + 1, for those who entered maintenance. For those who did not enter maintenance therapy, duration of maintenance will be defined as [minimum (date of first administration of [study drug] + 83 days, date of death, date of data cutoff) - (date of first administration of [study drug]) + 1.

Duration of [study drug] exposure (days) in maintenance phase = [minimum(Date of last week1 dose of [study drug] in maintenance + 41 days, date of death, date of data cutoff)] - (date of first week1 dose of [study drug] in maintenance) + 1.

	Demittion of last date of exposure of study drug					
Scenario	Definition of last date of exposure of study drug	sure of Example				
Carboplatin, Vincristine	The planned end date of the last cycle in which the last non-zero dose of the investigational drug was last administered (i.e. last week 1 date of administration + (planned interval duration of either induction or maintenance, as applicable)) If carboplatin or vincristine was permanently discontinued during induction, set the last date of exposure equal to the planned end date of induction,	Example 1: Subject discontinues during induction therapy. The last date of exposure is the first date o administration + 83 days.				
	If carboplatin or vincristine was permanently discontinued during maintenance, set the last date of exposure equal to the planned end date of the last cycle. last week 1 administration date + 41 days,	Example 2: Subject discontinues during maintenance therapy after receiving the week 45 dose. The week 43 (C dose 29/V dose 26) dose date was 21Jan2021. The last date of exposure is the 21Jan2021 + 41 days = 03Mar2021.				

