Dose of dabrafenib and trametinib will be defined in the units of mg, and taken from the dose administration CRF. Dose of carboplatin and vincristine will be defined in units of mg/m^2 , calculated as the administered dose received in mg/m^2 as taken from the dose administration CRF. **Dose intensity** (DI) for patients with non-zero duration of exposure is defined as follows:

DI (*unit of dose / unit of time*) = Actual Cumulative dose (*unit of dose*) / Duration of exposure to study treatment (*unit of time*).

For dabrafenib and trametinib, the unit of dose is mg and the unit of time is days; for carboplatin and vincristine, the unit of dose is mg/m^2 and the unit of time is weeks. [Note that for subjects < 12 kg in weight, the unit of dose for vincristine is mg/kg. If such subjects are enrolled in the study, their dosing data will be summarized separately.]

For patients who did not take any drug the DI is by definition equal to zero.

Planned dose intensity (PDI) is defined as follows:

PDI (*unit of dose / unit of time*) = Planned Cumulative dose (*unit of dose*) / Duration of exposure (*unit of time*).

For carboplatin, the PDI is 116.67 mg/m²/week, based on 6-week cycles with dosing of 175 mg/m² at weeks 1 to 4 only.

For vincristine, the PDI depends on the subject's weight and also on the treatment phase.

For subjects with weight ≥ 12 kg:

- during the induction phase, the PDI is 1.25 mg/m²/week, based on 1.5 mg/m² weekly *10 over 12 weeks.
- during the maintenance phase, the PDI is 0.75 mg/m²/week, based on 1.5 mg/m² weekly *3 over 6 weeks.

For subjects with weight < 12 kg:

• during the induction phase, PDI is 0.033 mg/kg/week, based on 0.05 mg/kg weekly *10 over 12 weeks.

Novartis	Confidential	Page 30
SAP	30-Sep-2021 (6:19)	CDRB436G2201

• during the maintenance phase, the PDI 0.025 mg/kg/week, based on 0.05 mg/kg weekly *3 over 6 weeks.

Relative dose intensity (RDI) is defined as follows:

RDI (%) = [DI (unit of dose / unit of time) / PDI (unit of dose / unit of time)] x 100.

DI and RDI will be summarized separately for each of the study treatment components, using the duration of exposure of each of the components. DI and RDI will be summarized separately for induction and maintenance phase for carboplatin and vincristine.

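### In both LGG SAPs the by-phase chemotherapy formula for patients who never entered maintenance is labelled maintenance where induction is meant

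*SAP*

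**What the plan says.** All references are to the LGG SAP. The wording at issue is the same in Amendment 1 and in the final SAP.

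- **By-phase duration (Section 2.4.1).** For patients who entered maintenance, induction runs from the first dose to the day before the first maintenance dose. The next sentence covers the others: "For those who did not enter maintenance therapy, duration of maintenance will be defined as" the minimum of first dose + 83 days, death and cut-off, minus the first dose, plus 1. A separate maintenance formula follows, which starts from a week 1 maintenance dose.
- **Induction rule (same section).** If a patient does not go on to maintenance, "the last date of exposure is the date of first administration (of carboplatin or vincristine) in induction + 83 days". If death or cut-off comes first, "the date will be capped at the date of death or data cutoff".
- **Table 2-7.** For discontinuation during induction: "set the last date of exposure equal to the planned end date of induction". Example 1 gives first administration + 83 days.
- **Maintenance paragraph.** Maintenance "will be identified by having at least 9 non-zero doses of Carboplatin, or at least 11 non-zero doses of Vincristine". The + 41-day rule in this paragraph concerns maintenance cycles but is said to apply to the induction phase.
- **Dose intensity (DI).** It is defined for any patient with a non-zero duration, and "DI and RDI will be summarized separately for induction and maintenance phase for carboplatin and vincristine".
- **Crossover.** The exposure caps are death and cut-off, with loss to follow-up added in Table 2-7. Crossover is not among them. For safety reporting, Section 2.1.1 says that if crossover starts within 30 days of the last dose, "the on-treatment period will end on the day before the first dose of crossover treatment". The Crossover Phase section (2.14 in Amendment 1, 2.13 in the final SAP) limits randomized-phase analyses, other than OS, to data before crossover.

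**The concern.** The formula gives time in maintenance to patients who, by its own condition, had none. It is also the only by-phase formula for these patients, so if it is read as maintenance, the paragraph offers no induction duration for them.

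No later rule stops this. Neither SAP restricts maintenance duration, DI or RDI to patients with a maintenance dose. The rule that DI is zero for patients who took no drug, if applied by phase, gives the same zero. A literal program would therefore place early stoppers in the lowest maintenance RDI category and remove them from the by-phase induction duration.

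At stake is the table that readers use to judge how fully the comparator was delivered in each phase. The reverse slip in the maintenance paragraph makes the section harder to read correctly. The final SAP revised a nearby figure (vincristine planned dose intensity in induction below 12 kg, from 0.033 to 0.042 mg/kg/week) but left both phase labels as they were.

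**Working it through.** **1. The plan's own worked examples (Tables 2-10 and 2-11) reproduce.**

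- Carboplatin induction: 01Jan2016 to 30Mar2016 = 90 days = 12.86 weeks. DI = 1200 / 12.86 = 93.3. RDI = 93.3 / 116.67 = 80%, as stated.
- Carboplatin maintenance: 14May2016 + 41 days = 24Jun2016. From 31Mar2016 that is 86 days = 12.29 weeks. RDI is 97.7% unrounded, or 97.6% with the SAP's rounded DI of 113.9, as stated.
- Vincristine: induction RDI 80.9%; maintenance 42 days and RDI 66.7%, as stated.

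Both examples follow patients who entered maintenance, so neither exercises the faulty sentence.

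**2. The faulty sentence, taken literally.** For a patient who stops in induction, with no earlier death or cut-off:

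- Duration = (first dose + 83) − first dose + 1 = 84 days = 12 weeks, labelled maintenance.
- Maintenance dose = 0, so carboplatin DI = 0 / 12 = 0 and RDI = 0 / 116.67 = 0%.

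**3. The same patient under the induction rule and Table 2-7, Example 1.** Induction = 84 days = 12 weeks, with no maintenance duration or maintenance RDI. With 4 of the 8 planned carboplatin doses, induction RDI = (4 × 175 / 12) / 116.67 = 50%. With all 8 it is 100%. These are sensible values and show that induction is meant.

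**4. Scale, if programmed literally.** The number of patients who never enter maintenance is not in the documents. Assume 34 controls (102 randomized 2:1), all treated, of whom 2 to 8 never enter maintenance, and a true mean maintenance RDI of 90% among those who do.

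- Mean with 2 non-entrants: 90% × 32/34 = 84.7%.
- Mean with 8 non-entrants: 90% × 26/34 = 68.8%.
- Added to the lowest RDI category: 2/34 = 5.9% to 8/34 = 23.5% of patients.

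**5. Crossover and duration.** Exposure is credited to the planned end of the cycle, 42 days from the last week 1 maintenance dose. If crossover began 28 days after that dose (an assumption; no timing is given), 42 − 28 = 14 credited days would overlap with dabrafenib plus trametinib.

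**6. Crossover and RDI.** The planned intensity of 116.67 mg/m²/week is already averaged over the rest weeks. A fully dosed last carboplatin cycle is 4 × 175 = 700 mg/m².

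| Duration used | Weeks | DI (mg/m²/week) | RDI |
|---|---|---|---|
| 42 days (as planned) | 6 | 116.67 | 100% |
| 35 days (capped) | 5 | 140 | 120% |
| 28 days (capped) | 4 | 175 | 150% |

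So the planned interval gives the right RDI, and a crossover cap in that calculation would distort it.

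**The case against.** The strongest reply is that this is a slip in one word that a careful programmer would resolve. The sentence sits in the induction paragraph and uses the 83-day induction rule. The real maintenance formula comes next and needs a dose these patients never had, and the dose-count rule keeps them out of maintenance. That stands as to intent. It does not make the sentence right: this is an operative formula, and the two SAPs repeat it unchanged.

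Three stronger readings are tempting, but the documents do not support them.

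- *Induction duration is undefined for early stoppers.* This is true only of the by-phase formula read literally. The induction rule and Table 2-7 fix the end date.
- *Control-arm exposure as a whole is wrong.* Overall duration is derived separately, for example "Duration of exposure to carboplatin overall (days) = (last date of exposure to carboplatin as defined in table 2.7"), and Table 2-7 treats discontinuation in induction correctly.
- *The missing crossover cap makes RDI wrong.* It does not, as step 6 shows. The SAP also keeps the planned interval for chemotherapy DI and RDI at death, so crediting planned rest is deliberate.

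Nor can early stoppers be assumed to be those who tolerated chemotherapy worst; patients may stop in induction for other reasons, including progression. Finally, the on-treatment rule in Section 2.1.1 serves safety reporting, so it does not by itself contradict planned-cycle exposure.

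**Conclusion.** The by-phase formula is wrong as written in both LGG SAPs. Its result is an induction duration carrying a maintenance label. Followed literally, it gives each patient who never entered maintenance up to 84 days of maintenance and a 0% maintenance RDI, and removes that patient from the by-phase induction duration. The effect on a reported mean, such as the fall from 90% to between 84.7% and 68.8% in step 4, depends on assumed counts and on literal programming; it is not a prediction.

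The reach is limited to descriptive by-phase exposure rows. Overall duration of each drug, ORR, PFS, OS, the hypothesis tests and the adverse event periods are untouched.

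The crossover point is smaller. Credited chemotherapy exposure may overlap with crossover treatment in a descriptive duration, and the SAP does not say how this fits its pre-crossover rule. The size cannot be worked out because no crossover timing is given.

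**What to change.** In Section 2.4.1 of both LGG SAPs:

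1. In the sentence for patients who did not enter maintenance, replace duration of maintenance with duration of induction.
2. In the maintenance paragraph, correct the reverse slip so that the + 41-day rule refers to the maintenance phase.
3. State that maintenance duration, DI and RDI are calculated only for patients with at least one maintenance dose.
4. For descriptive duration of exposure only, state how planned-cycle exposure is to be reconciled with the pre-crossover rule in the Crossover Phase section. If a crossover cap is added, exclude it explicitly from the duration used for DI and RDI, as is already done for death.

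The cost is two label corrections and one clarifying sentence. If the cap is adopted, one date is added to the exposure program, together with its exemption for DI and RDI. If the tables have already been produced, check which reading the program followed.

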2.5 Analysis of the primary objective

The primary objective of the LGG cohort is to compare the antitumor activity of dabrafenib in combination with trametinib versus the carboplatin and vincristine, as measured by overall response rate (ORR) to study treatment by central independent review assessment using RANO criteria, in children and adolescent patients with BRAF V600 mutation positive LGG whose tumor is unresectable and who require treatment.

2.5.1 **Primary endpoint**

ORR is defined as the proportion of patients with best overall response (BOR) of confirmed complete response (CR) or partial response (PR) according to RANO criteria (see Appendix 3 of the study protocol). ORR will be calculated based on the FAS using central independent review of tumor assessment data. Only tumor assessments performed before the start of any further antineoplastic therapy (i.e. any additional secondary antineoplastic therapy or surgery) will be considered in the assessment of BOR. See Appendix 5.5 for primary estimand definition.

Best overall response

The BOR will be assessed based on reported responses across all evaluation time points. Both CR and PR must be confirmed by repeat assessments performed not less than 4 weeks after the criteria for response are first met. The next scheduled assessment may be used for purposes of confirmation of response. In the absence of a confirming scan 4 weeks later, this response will be considered only stable disease.

BOR for each patient is determined from the sequence of overall responses according to the following rules, up to progression:

- CR = at least two determinations of CR at least 4 weeks apart before progression
- PR = at least two determinations of PR or better at least 4 weeks apart before progression (and not qualifying for a CR)
- SD = requires at least one SD assessment (or better) determined at or beyond the second regularly scheduled tumor assessment (nominally week 16 i.e >= 105 days allowing for the ±1 week visit window) from randomization (and not qualifying for CR or PR).
- PD = progression after start of study treatment (and not qualifying for CR, PR or SD).
- UNK = all other cases (i.e. not qualifying for confirmed CR or PR and without SD at or beyond the second regularly scheduled post-baseline tumor assessment or progression)

If a patient receives any further anti-neoplastic therapy while on study, any subsequent assessments will be excluded from the BOR determination for the primary endpoint. Further anti-neoplastic therapies will be identified via protocol deviations or from the data collected on 'Anti-neoplastic therapies since last date of study drug' as appropriate.

Novartis	Confidential	Page 37
SAP	30-Sep-2021 (6:19)	CDRB436G2201

2.5.2 Statistical hypothesis, model, and method of analysis

The primary efficacy analysis in the LGG cohort is the comparison of ORR based on independent review assessment between the two treatment arms. The following statistical hypothesis will be tested:

 $H_{01}: ORR_t \leq ORR_c$ vs. $H_{A1}: ORR_t > ORR_c$

where ORR_t is the ORR in the Trametinib plus Dabrafenib arm and ORR_c is the ORR in the control arm (carboplatin with vincristine). The analysis to test these hypotheses and compare the two treatment groups will consist of a Mantel Haenszel chi-square test at one-sided 2.5% level of significance.

The primary efficacy analysis will be performed on the FAS.

ORR will be summarized using descriptive statistics (N, %) by treatment arm along with twosided exact binomial 95% CIs (Clopper and Pearson 1934). The Odds ratio (dabrafenib + trametinib vs carboplatin + vincristine) and it's 95% confidence interval will be determined by logistic regression. Note that there is a possibility that the confidence interval for the odds ratio from the logistic regression may be inconsistent with the primary test.

